1.1. Synopsis

Protocol Title:

A Phase 3, Open-Label, Parallel-Group, 2-Arm Study to Investigate Amyloid Plaque Clearance with Donanemab Compared with Aducanumab-avwa in Participants with Early Symptomatic Alzheimer's Disease

Brief Title:

A Study to Investigate Amyloid Plaque Clearance with Donanemab Compared with Aducanumab-avwa in Participants with Early Symptomatic Alzheimer's Disease

Rationale:

Study I5T-MC-AACN (AACN) is a Phase 3, open-label, head-to-head study to evaluate the superiority of donanemab to aducanumab in participants with Early Symptomatic AD.

The amyloid hypothesis of AD postulates that the production and deposition of A β is an early and necessary event in the pathogenesis of AD (Selkoe 2000). Both donanemab and aducanumab have previously demonstrated the ability to reduce brain amyloid plaque burden and potentially slow clinical decline (Sevigny et al 2016; Mintun et al 2021; Aducanumab USPI, 2021). Recently, the FDA approved aducanumab, in the US, under accelerated approval for the treatment of AD based on its ability to reduce amyloid plaque burden (Aducanumab USPI, 2021). The current study aims to evaluate the superiority of donanemab to aducanumab on amyloid plaque clearance in participants with early symptomatic AD.

Objectives, Endpoints, and Estimands:

Objectives	Endpoints
Co-Primary	
To assess the superiority of donanemab versus aducanumab on complete brain amyloid plaque clearance in participants with early symptomatic AD.	Superiority of percentage of participants who reach complete amyloid plaque clearance on florbetapir F18 PET scan on donanemab versus aducanumab at 6 months.
To assess the superiority of donanemab versus aducanumab on complete brain amyloid plaque clearance in the intermediate tau subpopulation of participants with early symptomatic AD.	Superiority of percentage of participants who reach complete amyloid plaque clearance on florbetapir F18 PET scan in the intermediate tau subpopulation on donanemab versus aducanumab at 6 months.

Key Secondary	
To assess the superiority of donanemab versus aducanumab on degree of brain amyloid plaque reduction.	
Superiority of mean absolute change from baseline in brain amyloid plaque on florbetapir F18 PET scan for donanemab versus aducanumab at:
 
 • 6 months • 12 months, and • 18 months.
To assess the superiority of donanemab versus aducanumab in time to reach complete amyloid plaque clearance.	Time to reach complete amyloid plaque clearance on donanemab versus aducanumab.
Other Secondary	
To assess the superiority of donanemab versus aducanumab on degree of brain amyloid plaque reduction.	
Superiority of mean percent change from baseline in brain amyloid plaque on florbetapir F18 PET scan for donanemab versus aducanumab at:
 
 • 6 months • 12 months, and • 18 months.
To assess the non-inferiority of donanemab versus aducanumab on degree of brain amyloid plaque reduction.	
Non-inferiority of mean absolute change from baseline in brain amyloid plaque on florbetapir F18 PET scan at:
 
 • donanemab 6 months vs aducanumab 12 months, and • donanemab 6 months vs aducanumab 18 months.
To assess the superiority of donanemab versus aducanumab on complete brain amyloid plaque clearance.	
Superiority of percentage of participants who reach complete amyloid plaque clearance on florbetapir F18 PET scan on donanemab versus aducanumab at:
 
 • 12 months, and • 18 months.

To assess the superiority of donanemab versus aducanumab on complete brain amyloid plaque clearance in the intermediate tau subpopulation.	Superiority of percentage of participants who reach complete amyloid plaque clearance on florbetapir F18 PET scan in the intermediate tau subpopulation on donanemab versus aducanumab at: 
 • 12 months, and • 18 months.
To assess the superiority of donanemab versus aducanumab on degree of brain amyloid plaque reduction in the intermediate tau subpopulation.	Superiority of mean absolute change from baseline in brain amyloid plaque on florbetapir F18 PET scan in the intermediate tau subpopulation for donanemab vs aducanumab at: 
 • 6 months • 12 months, and • 18 months.
To assess the superiority of donanemab versus aducanumab on degree of brain amyloid plaque reduction.	Superiority of change from baseline in brain amyloid plaque reduction on florbetapir F18 PET scan for donanemab 6 months vs aducanumab 12 months.
To evaluate the safety and tolerability of donanemab vs aducanumab	Characterization of standard safety assessments: 
 • Spontaneously reported AEs • Clinical laboratory tests • MRI (ARIA and emergent radiological findings) • Serious hypersensitivity reactions • C-SSRS

Abbreviations: AD = Alzheimer's disease; AE = adverse event; ARIA = amyloid-related imaging abnormalities; C-SSRS = Columbia Suicide-Severity Rating Scale; MRI = magnetic resonance imaging; PET = positron emission tomography.

NOTE: Other pre-specified, non-gated endpoints not listed will be detailed in the SAP.

Overall Design

Study I5T-MC-AACN (AACN) is a Phase 3, open-label, head-to-head study to evaluate the superiority of donanemab to aducanumab in participants with early symptomatic AD.

Brief Summary:

Study AACN is a multicenter, randomized, open-label, head-to-head, Phase 3 study of donanemab compared to aducanumab in participants with early symptomatic AD.

Participants who meet entry criteria will be randomized in a 1:1 ratio to 1 of the following treatment groups:

- donanemab: 700 mg IV Q4W for first 3 doses and then 1400 mg IV Q4W
- aducanumab: Refer to PI/routine clinical practice

The maximum total duration of study participation for each participant, including screening and the post-treatment follow-up periods, is up to 127 weeks:

- Lead-In: any time prior to complete screening
- Complete Screening: up to 7 weeks
- Open-label study period: 76 weeks
- Follow-Up: up to 44 weeks

The maximum duration of treatment is 72 weeks.

Scheduled Reduction of Donanemab

Participants randomized to donanemab whose amyloid plaque reduction as measured by florbetapir F18 PET scans at Visit 8 (Week 24) or Visit 15 (Week 52) meets criteria will stop donanemab infusions but continue all other assessments for the remaining duration of the open-label period and short-term follow-up period. These dose reduction rules are defined by the sponsor.

Participants randomized to aducanumab will continue monthly infusions throughout the open-label period, regardless of amyloid plaque reduction on florbetapir F18 PET scans.

Participant randomization will be stratified by amyloid burden at baseline and ApoE ϵ 4 status (noncarrier/heterozygous/homozygous).

Number of Participants:

Approximately 200 participants will be randomly assigned to study intervention.

Intervention Groups and Duration:

[figure not shown]
Intervention Name	donanemab	aducanumab
Dosage Level(s)	700 mg IV Q4W for first 3 doses and then 1400 mg IV Q4W ^a	Refer to PI/routine clinical practice
Route of Administration	IV infusion	IV infusion
Use	experimental	active-comparator

Abbreviations: IV = intravenous; PI = package insert; Q4W = once every 4 weeks.

^a Participants randomized to donanemab whose amyloid plaque reduction as measured by florbetapir F18 PET scans at Visit 8 (Week 24) or Visit 15 (Week 52) meets criteria will stop donanemab infusions but continue all other assessments for the remaining duration of the open-label period and short-term follow-up period. These dose reduction rules are defined by the sponsor.

Data Monitoring Committee: Yes

1.2. Schema

Visit	601	1	2	3	4	5	6	7	8	9	10	11	12	13	14	15	16	17	18	19	20	21	801-804
Week		-7	0	4	8	12	16	20	24	28	32	36	40	44	48	52	56	60	64	68	72	76	84-120

Abbreviations: IV = intravenous; mg = milligrams; Q4W = every 4 weeks.

Note: V601 is optional. For participants who do not complete V601, procedures will be included in V1.

Randomization occurs at V2.

^a Participants whose amyloid plaque reduction as measured by florbetapir F18 PET scans at Visit 8 (Week 24) or Visit 15 (Week 52) meets criteria will stop donanemab infusions but continue all other assessments for the remaining duration of the open-label period and short-term follow-up period. These dose reduction rules are defined by the sponsor.

1.3. Schedule of Activities (SoA)

Screening

	LEAD-IN SCREENING	COMPLETE SCREENING	Notes
Visit No.:	601*	1	V1 may be conducted over more than 1 day. *V601 is optional. If the participant's initial visit is V1, then perform all V601 procedures in addition to V1 procedures.
Day Relative to Randomization	Can be done any time prior to complete screening	-49 to -1	
Tolerance Interval for Visit (Days)	Can be done at any time	≤49 before V2	
Entry and Administrative			
Abbreviated (or Full) Informed Consent – participant	X		The Abbreviated Informed Consent grants consent only for procedures and assessments marked under V601.
Full Informed Consent – participant		X	Do not collect if Full Informed Consent was collected at V601.
Full Informed Consent – study partner	X		Study partner(s) are not required to complete the abbreviated Informed Consent.
Participant number assigned via IWRS	X		
Demographics	X		
Inclusion/exclusion review		X	
Physical/neurological examination		X	As described in the Manual of Operations.
Concomitant medications		X	
Preexisting conditions		X	
Assessments			
Height and weight		X	

	LEAD-IN SCREENING	COMPLETE SCREENING	Notes
Visit No.:	601*	1	V1 may be conducted over more than 1 day. *V601 is optional. If the participant's initial visit is V1, then perform all V601 procedures in addition to V1 procedures.
Day Relative to Randomization	Can be done any time prior to complete screening	-49 to -1	
Tolerance Interval for Visit (Days)	Can be done at any time	≤49 before V2	
ECG		X	Single, locally-read ECG. Unscheduled ECGs may be performed at the discretion of investigator.
Chemistry		X	Blood draw can be performed at either at V601 or V1. Collect all blood draws for screening at the same time.
Hematology		X	
ApoE		X	Blood draw can be performed at either at V601 or V1. Collect all blood draws for screening at the same time.
Entry Diagnostics			
MMSE	X		Participants who do not meet MMSE criteria are not to have any other screening procedures performed. Administer the MMSE prior to medical procedures that could be stressful to the participant (blood draws, etc.).
CDR	X		Administer the CDR prior to medical procedures that could be stressful to the participant (blood draws, etc.).

	LEAD-IN SCREENING	COMPLETE SCREENING	Notes
Visit No.:	601*	1	V1 may be conducted over more than 1 day. *V601 is optional. If the participant's initial visit is V1, then perform all V601 procedures in addition to V1 procedures.
Day Relative to Randomization	Can be done any time prior to complete screening	-49 to -1	
Tolerance Interval for Visit (Days)	Can be done at any time	≤49 before V2	
Screening PET Scans and MRI			
Florbetapir F18 PET scan		X	The participant should meet all other non-imaging eligibility criteria before the screening florbetapir F18 PET scan. Previous florbetapir F18 PET scans within 3 months of randomization may be acceptable. The acceptance of a historical scan is at the discretion of the sponsor.
MRI		X	The participant should meet all other non-imaging eligibility criteria before the screening MRI.

Abbreviations: ApoE = apolipoprotein E; CDR = Clinical Dementia Rating; C-SSRS = Columbia-Suicide Severity Rating Scale; ECG = electrocardiogram; IWRS = interactive web response system; MMSE = Mini-Mental State Exam; MRI = magnetic resonance imaging; PET = positron emission tomography; V = visit.

Visits 2 through 11

	Open-Label Study Period										Comments
Visit Number	2	3	4	5	6	7	8	9	10	11	
Weeks relative to first infusion	0	4	8	12	16	20	24	28	32	36	
Visit interval tolerance (days)		-7 to +10	±7	±7	±7	±7	±7	±7	±7	±7	
Entry and Administrative											
Inclusion and exclusion criteria, review and confirm	X										Inclusion and exclusion criteria should be confirmed at V2, prior to randomization and administration of the first dose of study intervention.
Randomization	X										
Brief Physical/Neurological Exam	X			X			X			X	As described in the Manual of Operations. Any clinically significant changes from baseline on brief physical/neurological examinations should be noted on the AE CRF.
Concomitant medications	X	X	X	X	X	X	X	X	X	X	
AEs	X	X	X	X	X	X	X	X	X	X	Any events that occur after signing the informed consent are considered AEs as defined in Section 10.3.
C-SSRS screening/baseline	X										
C-SSRS since last assessment			X		X		X		X		
Administer study intervention	X	X	X	X	X	X	X	X	X	X	See Section 6.1. Administration of study intervention (and treatment-related activities conducted in person) outside of the visit window is not a protocol deviation, unless 2 doses are administered within <21 days of each other. The participant should be observed for a minimum of 30 minutes following the end of each infusion.

	Open-Label Study Period										Comments
Visit Number	2	3	4	5	6	7	8	9	10	11	
Weeks relative to first infusion	0	4	8	12	16	20	24	28	32	36	
Visit interval tolerance (days)		-7 to +10	±7	±7	±7	±7	±7	±7	±7	±7	
Vital signs	X	X	X	X	X	X	X	X	X	X	
Vital signs include pulse rate, blood pressure, and temperature. Vitals should be measured after participant has been sitting for at least 5 minutes.
 
Vital signs are measured prior to and within 30 minutes after infusion for clinical management, and not recorded in the CRF.

Weight (for aducanumab participants only)	X	X	X	X	X	X	X	X	X	X	Weight is measured prior to dosing with aducanumab only and is not recorded in the CRF.
MRI		X		X			X			X	
MRI at V3 is to be performed and reviewed prior to V3 infusion and may occur no sooner than 21 days after the first infusion. If infusions are suspended after the first, second, or third dose, an MRI is to be performed and reviewed prior to the fourth infusion.
 
MRI at V5 is to be performed and reviewed prior to V5 infusion. The MRI should occur at least 14 days after infusion at V4 is administered, and may occur outside of the visit windows.
 
MRI at V8 is to be performed and reviewed prior to V8 infusion. The MRI should occur at least 14 days after infusion at V7 is administered, and may occur outside of the visit windows.
 
MRI at V10 is to be performed and reviewed prior to V10 infusion. The MRI should occur at least 14 days after infusion at V9 is administered, and may occur outside of the visit windows.
 
Unscheduled MRIs may be performed at the discretion of investigator, for example, if titration is delayed due to temporary suspension of infusions.

	Open-Label Study Period										Comments
Visit Number	2	3	4	5	6	7	8	9	10	11	
Weeks relative to first infusion	0	4	8	12	16	20	24	28	32	36	
Visit interval tolerance (days)		-7 to +10	±7	±7	±7	±7	±7	±7	±7	±7	
Flortaucipir F18 PET scan	X										Will not be used for eligibility. Participants have +/- 3 months from randomization to obtain flortaucipir results (either from pre-existing scan or new scan). PET scans must be performed ≥16 hours apart from each other. Previous flortaucipir F18 PET scans may be acceptable. The acceptance of a historical scan is at the discretion of the sponsor.
Florbetapir F18 PET scan							X				PET scans must be performed ≥16 hours apart from each other.
Laboratory Tests and Sample Collections	In the event that study intervention is delayed, all laboratory collections should occur on the same day as study intervention infusion – and should be collected prior to infusion.										
Hematology and clinical chemistry							X				Collect prior to infusion.
PK sample							X				Collect prior to infusion. Predose collections may be collected from the IV site prior to the infusion.
Immunogenicity (ADA) samples	X						X				Collect prior to infusion.
Stored Samples											
Genetics sample	X										Collect prior to infusion.
Exploratory biomarker samples	X						X				Collect prior to infusion.

Abbreviations: ADA = anti-drug antibody; AEs = adverse events; CRF = case reporting form; C-SSRS = Columbia-Suicide Severity Rating Scale; MRI = magnetic resonance imaging; PET = positron emission tomography; PK = pharmacokinetic; V = visit.

Visits 12 through 21 and Follow-Up

	Open-Label Treatment											Short-term Follow-up	Comments
Visit Number	12	13	14	15	16	17	18	19	20	21	ET	801-804^	^Visit 801 to 804 may be used for return to baseline ADA monitoring and other safety assessments at discretion of the sponsor and may be requested within the time period listed.
Weeks relative to first infusion	40	44	48	52	56	60	64	68	72	76	-	84-120	
Visit interval tolerance (days)	±7	±7	±7	±7	±7	±7	±7	±7	±7	±7	-	±14	
Entry and Administrative													
Brief Physical/Neurological Exam				X			X			X	X	X	As described in the Manual of Operations. Any clinically significant changes from baseline on brief physical/neurological examinations should be noted on the AE CRF.
Concomitant medications	X	X	X	X	X	X	X	X	X	X	X	X	
AEs	X	X	X	X	X	X	X	X	X	X	X	X	Any events that occur after signing the informed consent are considered AEs as defined in Section 10.3.
C-SSRS since last assessment	X		X		X		X		X		X	X	

	Open-Label Treatment											Short-term Follow-up	Comments
Visit Number	12	13	14	15	16	17	18	19	20	21	ET	801-804^	^Visit 801 to 804 may be used for return to baseline ADA monitoring and other safety assessments at discretion of the sponsor and may be requested within the time period listed.
Weeks relative to first infusion	40	44	48	52	56	60	64	68	72	76	-	84-120	
Visit interval tolerance (days)	±7	±7	±7	±7	±7	±7	±7	±7	±7	±7	-	±14	
Administer study intervention	X	X	X	X	X	X	X	X	X	X			See Section 6.1. Administration of study intervention (and treatment-related activities conducted in person) outside of the visit window is not a protocol deviation, unless 2 doses are administered within <21 days of each other. The participant should be observed for a minimum of 30 minutes following the end of each infusion.
Vital signs	X	X	X	X	X	X	X	X	X	X	X	X	Vital signs include pulse rate, blood pressure, and temperature. Vitals should be measured after participant has been sitting for at least 5 minutes. Vital signs are measured prior to and within 30 minutes after infusion for clinical management, and not recorded in the CRF.
Weight (for aducanumab participants only)	X	X	X	X	X	X	X	X	X				Weight is measured prior to dosing with aducanumab only and is not recorded in the CRF.

	Open-Label Treatment											Short-term Follow-up	Comments
Visit Number	12	13	14	15	16	17	18	19	20	21	ET	801-804^	^Visit 801 to 804 may be used for return to baseline ADA monitoring and other safety assessments at discretion of the sponsor and may be requested within the time period listed.
Weeks relative to first infusion	40	44	48	52	56	60	64	68	72	76	-	84-120	
Visit interval tolerance (days)	±7	±7	±7	±7	±7	±7	±7	±7	±7	±7	-	±14	
MRI		X											MRI at V13 is to be performed and reviewed prior to V13 infusion. The MRI should occur at least 14 days after infusion at V12 is administered, and may occur outside of the visit windows. Unscheduled MRIs may be performed at the discretion of investigator, for example, if titration is delayed due to temporary suspension of infusions.
Florbetapir F18 PET scan				X						X	X		Collect at ET only if ET occurs at 3 or more IP infusions after the last florbetapir F18 PET scan.
Laboratory Tests and Sample Collections	In the event that study intervention is delayed, all laboratory collections should occur on the same day as study intervention infusion - and should be collected prior to infusion.												
Hematology and clinical chemistry				X						X	X		Collect prior to infusion.
PK sample				X						X	X	X	Collect prior to infusion. Predose collections may be collected from the IV site prior to the infusion.
Immunogenicity (ADA) samples				X						X	X	X	Collect prior to infusion.

	Open-Label Treatment											Short-term Follow-up	Comments
Visit Number	12	13	14	15	16	17	18	19	20	21	ET	801-804^	^Visit 801 to 804 may be used for return to baseline ADA monitoring and other safety assessments at discretion of the sponsor and may be requested within the time period listed.
Weeks relative to first infusion	40	44	48	52	56	60	64	68	72	76	-	84-120	
Visit interval tolerance (days)	±7	±7	±7	±7	±7	±7	±7	±7	±7	±7	-	±14	
Stored Samples													
Exploratory biomarker samples				X						X	X		Collect prior to infusion.

Abbreviations: ADA = anti-drug antibody; AEs = adverse events; CRF = electronic case reporting form; C-SSRS = Columbia-Suicide Severity Rating Scale; ET = early termination; MRI = magnetic resonance imaging; PET = positron emission tomography; PK = pharmacokinetic; V = visit.

2. Introduction

Donanemab is an antibody directed at the pyroglutamate modification of the third amino acid of amyloid beta (N3pG A β) epitope that is present only in brain amyloid plaques. It is being studied for the treatment of AD. The mechanism of action of donanemab antibody is to target and remove deposited amyloid plaque, a key pathological hallmark of AD, via microglial-mediated clearance.

Aducanumab is a human anti-A β monoclonal antibody that selectively targets aggregated forms of A β , including soluble oligomers and insoluble fibrils (Ferrero et al 2016). It was recently approved, in the US, under accelerated approval for the treatment of AD (Aducanumab USPI, 2021).

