9.2. Analyses Sets

For the purposes of analysis, the following analysis sets are defined:

Participant Analysis Set	Description
Full analysis set / ITT analysis set	All randomized participants with baseline and at least one post-baseline amyloid PET scan. Participants will be included in the analyses according to the planned intervention.
Intermediate tau set	All randomized participants with baseline and at least one post-baseline amyloid PET scan and a baseline flortaucipir F18 PET scan meeting the intermediate tau criteria.

Participant Analysis Set	Description
Safety analysis set	All participants who are exposed to study intervention. Participants will be analyzed according to the intervention they actually received.

The full analysis and intermediate tau sets are used to analyze endpoints related to the amyloid plaque objectives and the safety analysis set is used to analyze the endpoints and assessments related to safety.

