9.3. Statistical Analyses

9.3.1. General Considerations

Statistical analysis of this study will be the responsibility of the Sponsor or its designee.

Unless otherwise noted, tests of treatment effects will be conducted at a 2-sided alpha level of 0.05 (or equivalently, a 1-sided 0.025 alpha level); 2-sided CIs will be displayed with a 95% confidence level. All tests of interactions between treatment and other factors will be conducted at an alpha level of 0.05.

A suitable approach such as Bretz's graphical approach may be utilized to provide strong control of the study wise Type I error rate for the primary and key secondary hypotheses at an alpha level of 0.05 (Bretz et al. 2009; Bretz et al. 2011). Details on the graphical approach and testing strategy will be specified in the SAP prior to the first participant visit.

All amyloid plaque analyses will follow the ITT principle unless otherwise specified. An ITT analysis is an analysis of data by the groups to which participants are assigned by random allocation, even if the participant does not take the assigned treatment, does not receive the correct treatment, or otherwise does not follow the protocol.

When change from baseline is assessed, participants will be included in the analysis only if both a baseline and a postbaseline measure are available. Unless otherwise defined, a baseline measure is the last nonmissing observation collected prior to the first administration of study medications. Endpoint is the last nonmissing postbaseline measurement.

To allow for sequential testing, database locks and the testing of corresponding primary and key secondary objectives are expected to occur after all randomized participants have had a chance to complete the scheduled 24-week PET scan, the scheduled 52-week PET scan, and the scheduled 76-week PET scan. Data collected during the immunogenicity and safety follow-up period will be summarized and analyzed separately.

Any change to the data analysis methods described in the protocol will require an amendment only if it changes a principal feature of the protocol. Any other change to the data analysis methods described in the protocol, and the justification for making the change, will be described in the SAP and the clinical study report. Additional exploratory analyses of the data will be conducted as deemed appropriate.

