10.7. Appendix 7: Flortaucipir F18 PET Imaging

Flortaucipir F18 PET scan will be performed after eligibility is established (Section 1.3).

No results will be provided to site investigators, participants, and study partners for the flortaucipir F18 scans. Any significant findings that may be of potential medical concern will be provided for appropriate follow-up

PET Scan-Specific Information

PET Scan Procedures

Specific imaging acquisition protocols designed to ensure consistency across sites will be provided in a PET Imaging Manual.

Scan Safety

The primary risk related to flortaucipir F18 PET is radiation exposure. Details on the amount of exposure estimated to occur on each imaging occasion and cumulatively are shown in the table below and will be provided in the ICF. The safety profile of flortaucipir has been well-characterized in clinical studies and is considered acceptable for a diagnostic radiopharmaceutical. Details on the clinical information to date regarding flortaucipir F18 exposure will be provided in the ICF. More detailed information about the known and expected benefits and risks of flortaucipir F18 can be found in the IB.

Participants must minimize movement during each PET procedure, which can last 10 to 30 minutes for each scan. Most state-of-the-art imaging systems are designed to reduce head motion and participant discomfort.

The table below shows the effective radiation dose of the Study AACN's PET scans.

	Effective Dose (mSv) per Scan ^a	Number of Scans in First Year ^b	Effective Dose (mSv) for Scans in First Year	Number of Scans in Second Year ^b	Effective Dose (mSv) for Scans in Second Year	Sum of Effective Dose (mSv) for Years 1 and 2
Flortaucipir F18 Scan (10 mCi IV)	9.10	1	9.10	0	0	9.10
Florbetapir F18 Scan (10 mCi IV)	7.43	2	14.86	2	14.86	29.72
Totals		3	23.96	2	14.86	38.82

Abbreviations: CT = computerized tomography; ED = early discontinuation; IV = intravenous infusion;
PET = positron emission tomography.

^a Dose shown includes radiation exposure from the radiotracer and assumes a nonclinical CT scan is obtained (estimated at 0.4 mSv) as part of the PET scan attenuation correction process when the scan is done on a PET/CT scanner. A clinical CT scan is not needed during the PET scan session and, because it will add additional radiation exposure, it is not recommended.

^b In the event of an ED scan, up to 1 additional florbetapir F18 scan may be received in 1 year.

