4.1. General Considerations

Statistical analysis of this study will be the responsibility of the Sponsor or its designee.

Unless otherwise noted, tests of treatment effects will be conducted at a 2-sided alpha level of 0.05 (or equivalently, a 1-sided 0.025 alpha level); 2-sided CIs will be displayed with a 95% confidence level. If relevant, tests of interactions between treatment and other factors will be conducted at an alpha level of 0.05.

Participant assignment to treatment will be stratified by ApoE ϵ 4 genotype, and baseline amyloid level. These factors will be included in analysis models unless otherwise stated.

All amyloid plaque analyses will follow the ITT principle unless otherwise specified. An ITT analysis is an analysis of data by the groups to which participants are assigned by random allocation, even if the participant does not take the assigned treatment, does not receive the correct treatment, or otherwise does not follow the protocol.

When change from baseline is assessed, participants will be included in the analysis only if both a baseline and a postbaseline measure are available. Unless otherwise defined, a baseline measure is the last non-missing observation collected prior to the first administration of study medications. Endpoint is the last non-missing post-baseline measurement.

To allow for sequential testing, database locks and the testing of corresponding primary and key secondary objectives are expected to occur after all randomized participants have had a chance to complete the scheduled 24-week PET scan, the scheduled 52-week PET scan, and the scheduled 76-week PET scan. If an interim analysis occurs, a database lock will additionally occur after a sufficient number of participants (for example, approximately 75-125) have had a chance to complete the scheduled 24-week PET scan. Data collected during the immunogenicity and safety follow-up period will be summarized and analyzed separately.

Any change to the data analysis methods described in the protocol will require a protocol amendment only if it changes a principal feature of the protocol. Any other change to the data analysis methods described in the protocol, and the justification for making the change, will be described in the SAP and the clinical study report. Additional exploratory analyses of the data will be conducted as deemed appropriate.

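### Does a tau PET scan taken after the first infusion count as the baseline scan that defines the intermediate tau co-primary set?

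*Protocol*

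**What the plan says.** Protocol 1.3 marks flortaucipir PET once, at Visit 2, and attaches a window: "Participants have +/- 3 months from randomization to obtain flortaucipir results (either from pre-existing scan or new scan". The same comment says that the scan plays no part in eligibility. Appendix 7 adds "Flortaucipir F18 PET scan will be performed after eligibility is established (Section 1.3", and its radiation table counts one flortaucipir scan in year one and none in year two.

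Visit 2 is Week 0. The schema notes "Randomization occurs at V2", and the schedule asks for this order at that visit: "Inclusion and exclusion criteria should be confirmed at V2, prior to randomization and administration of the first dose of study intervention". Infusions follow at Weeks 4, 8 and 12.

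Protocol 9.2 limits the intermediate tau set to participants who have, besides amyloid scans, "a baseline flortaucipir F18 PET scan meeting the intermediate tau criteria". SAP Section 3 sets the same requirement. Protocol 9.3.1 gives the default: "Unless otherwise defined, a baseline measure is the last nonmissing observation collected prior to the first administration of study medications". SAP 4.1 repeats it. In both documents the rule follows directly on a sentence about analyses of change from baseline.

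SAP 2.1 requires both co-primary tests to succeed. Protocol 9.5 expects about 90 participants per arm with a 6-month amyloid scan, about half of them with intermediate tau, and at least 98% power in each population.

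**The concern.** Taken one after the other, the passages seem to collide. The schedule accepts a tau scan up to three months after randomization, by which time as many as four infusions (Weeks 0, 4, 8 and 12) may have been given. The default rule would not call such a scan baseline, so a participant whose only tau scan came then would drop out of a co-primary set despite following the schedule exactly. Appendix 7 strengthens the impression: if eligibility is settled only at Visit 2, a new scan done afterwards falls on or after the day of first dosing.

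Two things would be at stake. The set could be smaller than the sample size section assumes, with no stated allowance for it. Alternatively, if late scans do count, a co-primary population in an open-label trial would be defined partly by measurements made on treatment.

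**Working it through.** **Reading the passages together**

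1. The default baseline rule yields to any other definition, and it sits among sentences on change from baseline. Tau PET is done once, so no change in it is analysed. A reader can fairly take the single Visit 2 scan, with its own window, as the baseline tau scan. A reader can equally apply the default literally, because the schedule comment never uses the word baseline. Both readings are open.
2. The sequence does not force late scans. Visit 1, up to 49 days before Visit 2, already carries an "Inclusion/exclusion review". A new scan may therefore fall between Visits 1 and 2, or on the day of Visit 2 before the infusion. Pre-existing scans may also be accepted. Only participants whose sole tau scan is post-dose are affected.

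**Size on the excluding reading**

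Inputs from Protocol 9.5: 6-month clearance 35.7% against 3.0%; 90 evaluable per arm; 50% with intermediate tau, so 0.50 × 90 = 45 per arm. Two-sided alpha is 0.05 (SAP 2.1).

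Pooled normal approximation:

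power = Φ{ [Δ√n − z·√(2·p̄(1 − p̄))] / √(p₁(1 − p₁) + p₂(1 − p₂)) }

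- Δ = 0.357 − 0.030 = 0.327 and p̄ = 0.1935
- √(2 × 0.1935 × 0.8065) = 0.5587
- √(0.357 × 0.643 + 0.030 × 0.970) = 0.5086
- z = 1.960, so z × 0.5587 = 1.095

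The plan's own figure comes first. At n = 45: (0.327 × 6.708 − 1.095) / 0.5086 = 2.16, which gives 98.5%. At n = 90 power exceeds 99.9%. Both agree with the stated minimum of 98%. The sponsor's mixed-model simulation cannot be rerun, so this is an approximation to it.

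The share of post-dose scans is not in the documents. The shares below are assumptions, with n = 45 × (1 − share), rounded down. SAP 4.4 calls for Firth's penalised logistic regression under quasi-complete separation. An aducanumab arm with no clearances is one such case, with probability 0.97ⁿ: 25% at n = 45 and 44% at n = 27. The last column therefore gives exact power of an unadjusted Firth likelihood-ratio test, used throughout.

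| Assumed share excluded | n per arm | Pooled formula | Firth likelihood ratio |
|---|---|---|---|
| 0% | 45 | 98.5% | 99.3% |
| 10% | 40 | 97.2% | 98.7% |
| 20% | 36 | 95.6% | 97.6% |
| 30% | 31 | 92.3% | 94.9% |
| 40% | 27 | 88.3% | 92.9% |
| 50% | 22 | 80.6% | 87.0% |

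If the optional interim takes place and the final test uses 0.02774 (SAP 4.9, information fraction 0.50), the pooled formula gives 97.1% at 45 per arm, 95.0% at 40 and 87.7% at 31.

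**Size on the including reading**

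Nobody is lost for a late scan, n stays at about 45, and the table does not apply.

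**The case for a change.** The strongest case for acting is that membership of a co-primary set should not be open to two readings, least of all in an open-label trial where someone could settle the matter late. The reserve is also thin: the pooled formula needs 43 per arm for 98%, against 45 planned, so losing 10% already takes that formula below the stated figure. Other Visit 2 collections, such as the anti-drug antibody and genetics samples, carry an instruction to collect before infusion; the tau scan does not. The Firth column is also the kinder one, because the SAP does not name the test statistic. A Wald test on the log odds ratio, with 0.5 added to every cell if any is zero, has only 69% power at 22 per arm.

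The ambiguity is real, and that part stands. Its reach is limited. The power loss arises under one reading only and at shares nobody has observed. On the excluding reading, membership depends on a scan made before treatment, so no bias or inflated error rate follows. The room for a choice driven by results is also narrow: Protocol 6.3 keeps post-baseline amyloid values scrambled or masked in the reporting database until the interim or the 6-month lock, and Appendix 7 keeps tau results from sites. The including reading would bring in some on-treatment scans, and the documents give no basis for judging whether up to four infusions would move a participant across the intermediate tau boundary.

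**Conclusion.** No change to the plan follows. This is an undefined term, not an error of design. Analysts deriving the set must decide what baseline means for a scan done once with its own window, and the documents already supply a workable default that gives a valid set. Settling the term would alter no scan, model or test.

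The size is small on plausible assumptions. On the excluding reading, pooled-formula power goes from 98.5% to 97.2% with 10% of the set lost, and to 92.3% with 30% lost. It falls below 90% only when the loss approaches 40%. On the including reading there is no loss. These figures rest on the planned clearance rates, 45 per arm, two-sided 0.05 and unadjusted tests; they would be lower at the reduced alpha that follows an interim. The conclusion would be less comfortable if a large part of the tau scans proved to be post-dose, but nothing in either document points that way.
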